4.2.4 Supplementary Analyses

The primary analysis will be supported by descriptive summaries including medians, geometric means and corresponding 95% CIs, Min, and Max for each serum collection time point. These summaries will be performed for both the Immunogenicity Analysis Set and the Safety Analysis Set. No windowing or imputation will be applied for this summary, as they will be presented by the visit at which the serum sample was acquired.

A responder analysis will be performed, with response analyzed by serum collection time point. Response defined separately for naïve subjects (Group 1) and experienced subjects (Groups 2 and 3) as follows:

- Group 1: having SARS-CoV-2 neutralizing antibody titers above the LLOQ, or
- Groups 2 and 3: having an at least 2-fold, 4-fold, and/or 6-fold increase from baseline SARS-CoV-2 neutralizing antibodies.

For Group 1, subjects are required to have a negative qualitative SARS-CoV-2 test at screening to enter the trial. Despite this, there is a chance they have positive neutralizing titer at baseline. In this case, response would be defined as an at least 2-fold increase from baseline in neutralizing titer.

Response rates will be summarized for the Immunogenicity Analysis Set by time point as well as overall for the Active Trial Period, and corresponding 95% CIs will be calculated using the Clopper-Pearson method. The response rate analysis will also be repeated for the Safety Analysis Set with subjects missing a value for a time point, and not having achieved a response at a previous timepoint, counted as non-responders. For the final CSR, an over response rate will be calculated inclusive of the FU visits in addition to the Active Trial Period rates.

The primary analyses will also be performed within sex (male vs. female) and age groups as supportive analyses: 18 to < 50 years, 50 to < 65 years, 65 to < 75 years, and \geq 75 years. These summaries will be performed for the Immunogenicity Analysis Set only.

4.3 Secondary Estimand Analyses

4.3.1.1 Definition of Endpoints

Percent of subjects reporting any SAE or AESI, as well as \geq Grade 3 AEs assessed as related to trial vaccine within 8 days after vaccination.

The second intercurrent event, discontinuation due to AEs from either the second vaccination (Group 1) or the trial (all groups), is relevant for this estimand. If it is confirmed by the investigator that the subject discontinues the trial within 8 days after vaccination due to AEs, the subject is considered having a related SAE/AESI/Grade 3 or higher AE regardless of the seriousness, severity, or causality of the AE for which the subject discontinued. This is consistent with the “composite” strategy.

4.3.1.2 Main Analytical Approach

For the Safety Analysis Set, the percent of subjects reporting any related SAE or AESI, as well as subjects reporting any related \geq Grade 3 AE within 8 days after any vaccination will be summarized, and the 95% CI will be calculated using the Clopper-Pearson method. For Group 1, this analysis will be performed by vaccination period and for the overall Active Trial Period.

4.3.1.3 Sensitivity Analyses

If any subject discontinues the trial within 8 days after vaccination due to AEs, a sensitivity analysis will be performed using the “treatment policy” strategy to handle the intercurrent event, where the subject will not be considered having a related SAE or AESI, or having a \geq Grade 3 AE assessed as related to trial vaccine, unless the specified AE leading to discontinuation meets one or more of these categories.

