9.14 Intercurrent Events

The second intercurrent event is relevant for this estimand. If it is confirmed by the investigator that the subject discontinues the trial within 8 days after vaccination due to AEs, the subject is considered having a related SAE/AESI/Grade 3 or higher AE regardless of the seriousness, severity, or causality of the AE for which the subject discontinued. This is consistent with the “composite” strategy.

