9.16 Sensitivity and Supportive Analyses

If any subject discontinues the trial within 8 days after vaccination due to AEs, a sensitivity analysis will be performed using the “treatment policy” strategy to handle the intercurrent event, where the subject will not be considered having a related SAE/AESI/Grade 3 or higher AE assessed as related to trial vaccine.

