This Statistical Analysis Plan (SAP) details the statistical methodology to be used in analyzing trial data and outlines the key statistical programming specifications. It describes the variables and populations, anticipated data transformations and manipulations, and other details of the analyses not provided in the trial protocol. The SAP is written based on recommendations from *ICH E3: Structure and Content of Clinical Study Reports*, and *ICH E9: Statistical Principles for Clinical Trials*. Table, figure and listing shells are described in a separate document.

This SAP will be followed completely for the analysis of data derived from the clinical trial. Changes to the protocol planned analyses are described in Section 4.7. If any unforeseen additional analyses are included in the clinical study report (CSR) they will be clearly described as additional, unplanned analyses in Section 4.7 if added prior to database lock, or to the equivalent section of the CSR if ad-hoc analyses are requested post-database lock.

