Intercurrent Events: Discontinuation due to AEs from either the second vaccination (Group 1) or the trial (all groups). If it is confirmed by the investigator that the subject discontinues the trial within 8 days after vaccination due to AEs, the subject is considered having a related SAE/AESI/Grade 3 or higher AE regardless of the seriousness, severity, or causality of the AE for which the subject discontinued. This is consistent with the “composite” strategy.

Note, including subjects who withdraw due to AEs within 8 days after vaccination as having had an SAE/AESI/Grade 3 or higher AE regardless of the seriousness, severity, or causality of the AE for which the subject discontinued will only occur for these secondary endpoints. The remaining summaries for safety will be presented as collected.

Population-level summary: Percent of subjects reporting any SAE or AESI assessed as related to trial vaccine within 8 days after vaccination, and percent of subjects reporting any Grade 3 or higher AE assessed as related to trial vaccine within 8 days after vaccination.

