4.7 Changes to Protocol-planned Analyses

The primary analysis has been updated to include only Groups 2 and 3 through the end of the Active Trial Period to assist in planning for the Phase 3 trial.

For neutralizing titer response in seropositive subjects, a threshold of ≥ 6 -fold increase has been added to the response summaries.

5 Subject Population Summaries

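### The treatment-policy sensitivity analysis of the two secondary safety endpoints is defined differently in protocol and SAP, and neither definition scores events as observed (low impact)

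*SAP*

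**What the plan says.** There are two secondary safety endpoints: related SAEs or AESIs, and related AEs of Grade 3 or higher, each within 8 days after vaccination.

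- **Main analysis (composite).** The documents agree. Under protocol 9.14, if a subject leaves the trial within 8 days because of an AE, "the subject is considered having a related SAE/AESI/Grade 3 or higher AE regardless of the seriousness, severity, or causality of the AE". SAP 4.3.1.1 has the same rule: "regardless of the seriousness, severity, or causality of the AE for which the subject discontinued".
- **Sensitivity analysis, protocol 9.16.** The strategy is labelled treatment policy and described as one "where the subject will not be considered having a related SAE/AESI/Grade 3 or higher AE assessed as related to trial vaccine". No exception is given.
- **Sensitivity analysis, SAP 4.3.1.3 and the secondary-endpoint entry in SAP 1.1.** Label and rule are the same, except that the subject is scored event-free "unless the specified AE leading to discontinuation meets one or more of these categories".
- **Record of changes.** The SAP introduction says: "Changes to the protocol planned analyses are described in Section 4.7". That section has two entries: "The primary analysis has been updated to include only Groups 2 and 3 through the end of the Active Trial Period" and "a threshold of ≥ 6 -fold increase has been added to the response summaries". Neither concerns the safety sensitivity rule.

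**The concern.** A treatment-policy strategy treats the intercurrent event as irrelevant to scoring: an event that was observed counts, whether or not the subject then left. Both documents use that label but let the discontinuation decide the score. The protocol forces the score to zero. The SAP forces it to zero unless one particular AE, the one that led to discontinuation, qualifies.

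The composite analysis counts every early AE discontinuation as an event, so it can exceed the observed rate. The sensitivity analysis is there to show the result without that addition. If its rule also removes observed events, it can report a rate below the one seen in the trial, and it can disagree with the AE tables in the same report. Because the two texts differ and the difference is not recorded, a reader cannot tell which rule was intended.

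**Working it through.** **Step 1: inputs.** The scoring rules come from protocol 9.14 and 9.16 and SAP 1.1, 4.3.1.1 and 4.3.1.3. The interval method, Clopper-Pearson at 95%, comes from protocol 9.15 and SAP 4.3.1.2. The planned group sizes of 30, 90 and 90 come from SAP 6. The documents give no expected rate for these endpoints or for early AE discontinuation, so there is no planned figure to reproduce.

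**Step 2: score one subject under each rule.** Take a subject who leaves the trial within 8 days because of an AE, and one endpoint. Ask whether the AE that led to discontinuation meets the endpoint definition, and whether any other AE within 8 days does. Read literally, with 1 = event:

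| Case | Discontinuing AE qualifies | Another AE qualifies | Composite | Protocol sensitivity | SAP sensitivity | As observed |
|---|---|---|---|---|---|---|
| a | no | no | 1 | 0 | 0 | 0 |
| b | no | yes | 1 | 0 | 0 | 1 |
| c | yes | no | 1 | 0 | 1 | 1 |
| d | yes | yes | 1 | 0 | 1 | 1 |

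- The protocol rule differs from the observed score in b, c and d.
- The SAP rule differs from it only in b.
- Protocol and SAP differ from each other in c and d.

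Case b can arise. Protocol 8.14 treats solicited local AEs as vaccine-related by definition, and protocol 8.3 includes solicited symptoms among AEs. If solicited AEs count towards the endpoint, a subject with Grade 3 injection-site pain who leaves because of Grade 2 nausea is case b for the Grade 3 endpoint.

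**Step 3: the two endpoints.** Suppose the discontinuing AE is a related, non-serious Grade 3 event that is not an AESI, and nothing else qualifies. The observed scores are 1 on the Grade 3 endpoint and 0 on the SAE/AESI endpoint. If the exception is applied per endpoint, the SAP gives the same scores. If meeting any one category lifts the rule for both, the SAE/AESI score becomes 1. The wording does not exclude the second derivation.

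**Step 4: size for one affected subject.** The number affected is an assumption; suppose it is one subject, with no other events in the group. Clopper-Pearson limits for x events in n:

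- x = 0: lower 0; upper 1 − 0.025^(1/n). For n = 90 the upper limit is 4.0%; for n = 30 it is 11.6%.
- x = 1: lower 1 − 0.975^(1/n); upper is the 0.975 quantile of Beta(2, n − 1). For n = 90 this gives 0.03% to 6.0%; for n = 30, 0.08% to 17.2%.

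| Group | As observed | As the rule would report it |
|---|---|---|
| 2 or 3 (n = 90) | 1/90 = 1.1% (0.03–6.0) | 0/90 = 0% (0–4.0) |
| 1 (n = 30) | 1/30 = 3.3% (0.08–17.2) | 0/30 = 0% (0–11.6) |

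Under the protocol rule, one subject in case b, c or d produces this shift. Under the SAP rule it takes a subject in case b.

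**The case against.** The strongest defence is that the intent is plain. Set against a composite rule that counts a subject merely for leaving, the sensitivity wording probably means that leaving is not by itself counted as an event. The SAP exception fits that reading, and the SAP introduction commits to following the SAP in full, so the bare protocol rule would not be run. This largely stands as an account of intent. But neither text states it, and a programmer who follows the SAP sentence literally gets the wrong score in case b.

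The second defence is that little depends on the result. The analysis runs only if someone leaves within 8 days because of an AE, no hypothesis is tested, the composite main analysis counts all such subjects, and "The remaining summaries for safety will be presented as collected". All of that stands, and it is why the impact is low.

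Three stronger readings are tempting, and the documents do not support them:

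- A reader might infer that both documents erase observed events whenever a subject leaves because of an AE. That is true of the protocol wording only. The SAP clause keeps the event when the discontinuing AE qualifies (cases c and d).
- A reader might infer that the composite and sensitivity rates fail to bracket the observed rate. For dropped events they do bracket it: in every row of the table the observed score lies between the two, or equals one of them. Bracketing could fail only under the cross-endpoint reading in Step 3, which adds an event rather than removing one. That reading is left open by the wording but is nowhere stated.
- A reader might infer that safety events would be hidden. They would not: the AE tables and listings in SAP 4.5.2 still show them.

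**Conclusion.** The point holds as a definition error with low impact. Protocol 9.16 and SAP 4.3.1.3/1.1 give different scores for a subject whose discontinuing AE is itself a related SAE, a related AESI or a related Grade 3 or higher AE, and SAP 4.7 does not record the change. Neither rule is treatment policy: the protocol drops any observed qualifying event in these subjects, and the SAP drops one when it is a different AE from the one that led to discontinuation. The SAP exception also leaves open whether the endpoints are scored separately.

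The illustrated size is one event reported as none: 1.1% as 0% in a group of 90, or 3.3% as 0% in a group of 30. This assumes one affected subject and no other events in the group. Under the SAP such a subject must leave the trial within 8 days because of a non-qualifying AE and also have a separate qualifying AE in that window. The documents give no basis for saying how often that would occur. The main analysis is unaffected.

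**What to change.** In SAP 4.3.1.3 and 1.1, and in protocol 9.16 at the next amendment, replace the rule with wording to this effect: *For the treatment-policy sensitivity analysis, each subject is scored separately on each endpoint from all AEs recorded with onset within 8 days after vaccination, as assessed by the investigator, whether or not the subject discontinued and whichever AE led to discontinuation.* Add an entry for the change to SAP 4.7.

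The cost is a few lines of text. The derivation becomes simpler, because it uses the recorded AE attributes and does not need to identify the AE that led to discontinuation. No additional data are required.

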4.3.1.4 Supplementary Analyses

The secondary estimand analysis will be repeated for the percent of subjects reporting any related SAE or AESI, as well as subjects reporting any related \geq Grade 3 AE within 29 days after any vaccination as a supplementary endpoint.

Additional analyses of AEs will be included as part of the safety analyses.

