
Secondary
 
To assess the safety and tolerability of the ABNCoV2 vaccine in adult seropositive and seronegative subjects.
	
Secondary:
 
 Subjects reporting any Serious Adverse Events (SAEs) or Adverse Events of Special Interest (AESIs) assessed as related to trial vaccine within 8 days after vaccination Subjects reporting any Grade 3 or higher Adverse Events (AEs) assessed as related to trial vaccine within 8 days after vaccination For the primary analysis of these endpoints, if the investigator confirms the subject discontinues the trial within 8 days after vaccination due to AEs, the subject is considered having a related SAE/AESI/Grade 3 or higher AE regardless of the seriousness, severity, or causality of the AE for which the subject discontinued. This is consistent with the “composite” strategy. 
Sensitivity Analyses:
 
 Subjects who discontinue the trial within 8 days after vaccination due to AE will be analyzed using the “treatment policy” strategy to handle the intercurrent event, where the subject will not be considered having a related SAE/AESI/Grade 3 or higher AE assessed as related to trial vaccine, unless the specified AE leading to discontinuation meets one or more of these categories.

Objectives	Endpoints
	
Supportive Endpoints:
 
 Subjects reporting any SAE or AESI, regardless of relationship, within 29 days after vaccination. Subjects reporting any Grade 3 or higher AEs assessed as related to trial vaccine within 29 days after vaccination. Subjects reporting solicited local AEs within 8 days after vaccination. Subjects reporting solicited general AEs within 8 days after vaccination.

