In general, AEs will be summarized by SOC, PT, and group for the Safety Analysis Set in the Active Trial Period. AEs occurring after the Active Trial Period during the FU period will be included in the AE listings. AEs occurring between ICF signature and first vaccination will be

considered Baseline Signs and Symptoms and will be reported similarly to medical history events.

For Group 1, summaries will also be included by period for Vaccination Period 1, Vaccination Period 2, and the overall Active Trial Period. For the overall Active Trial Period, event counts will include events from both vaccination periods in the case a subject experiences the same event multiple times.

Groups 2 and 3 will be summarized for the Active Trial Period, separately from Group 1.

An overall summary of solicited and unsolicited AEs including subject counts, event counts, percentages (of subjects only) will be created for the following event categories:

Solicited and Unsolicited AEs

- All AEs
- SAEs
- AEs Leading to Withdrawal
- Fatal AEs

Solicited AEs

- Local AEs
 - \geq Grade 3
 - Leading to Deferral or Discontinuation of Vaccine
 - SAEs
- General AEs
 - \geq Grade 3
 - Related
 - Related \geq Grade 3
 - Leading to Deferral or Discontinuation of Vaccine
 - SAEs

Unsolicited AEs

- All AEs
 - Related
 - \geq Grade 3
 - Related \geq Grade 3

- Leading to Withdrawal
- SAEs
 - Within 8 Days After Vaccination
 - Within 29 Days after Vaccination*
 - Related SAEs
 - Fatal
- AESIs
 - Within 8 Days After Vaccination
 - Within 29 Days after Vaccination*
 - Related AESIs
- Related AEs \geq Grade 3
 - Within 8 Days After Vaccination
 - Within 29 Days after Vaccination*

*Within 29 days summaries includes through the day prior to second vaccination for Group 1 Vaccination Period 1, or from the last/single booster vaccination through the end of the Active Trial Period for all groups. The window for the end of the Active Trial Period visit is 28-35 days post last/single booster vaccination.

Summary tables for unsolicited AEs by SOC and PT will be presented including subject and event counts and percentages (of subjects only) for the Active Trial Period:

- AEs
- Related AEs
- AEs \geq Grade 3
- Related AEs \geq Grade 3
 - Related AEs \geq Grade 3 Occurring within 8 Days of any Vaccination
 - Related AEs \geq Grade 3 Occurring within 29 Days of any Vaccination*
- Non-serious AEs in $> 5\%$ of Subjects
- SAEs
- Related SAEs
 - Related SAEs Occurring within 8 Days of any Vaccination

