 - Related SAEs Occurring within 29 Days of any Vaccination*
- AESIs

- Related AESIs
 - Related AESIs Occurring within 8 Days of any Vaccination
 - Related AESIs Occurring within 29 Days of any Vaccination*
- AEs Leading to Discontinuation of Active Trial Period

*Within 29 days summaries includes through the day prior to second vaccination for Group 1 Vaccination Period 1, or from the last/single booster vaccination through the end of the Active Trial Period for all groups. The window for the end of the Active Trial Period visit is 28-35 days post last/single booster vaccination.

Tables summarized by SOC and PT will be sorted in order of descending incidence of SOCs in the overall column, and descending order of incidence of PTs within the SOCs. For subject level frequencies and percentages, subjects experiencing an event more than once will be counted only once within SOC and PT, however all events will be counted in the event column.

All AEs will be listed by group, subject, onset date, SOC, and PT. Separate listings will be created for SAEs, AESIs, AEs \geq Grade 3, and AEs leading to discontinuation of the Active Trial Period. Listings will include any AEs collected during the FU period.

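### SAP 4.3.1.4 analyses the 29-day SAE/AESI endpoint for related events only, although both documents define it without regard to causality, and SAP 4.7 does not declare the difference

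*SAP*

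**What the plan says.** **Endpoint.** SAP 1.1 lists as a supportive endpoint: "Subjects reporting any SAE or AESI, regardless of relationship, within 29 days after vaccination". Protocol 1.3 (Safety Endpoints) has the same definition. In both lists the next item, Grade 3 or higher AEs within 29 days, is limited to events related to vaccine.

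**Analysis.** SAP 4.3.1.4 plans: "The secondary estimand analysis will be repeated for the percent of subjects reporting any related SAE or AESI", together with related Grade 3 or higher AEs, both within 29 days, and calls the result a supplementary endpoint. The analysis being repeated is that of 4.3.1.2, where "the 95% CI will be calculated using the Clopper-Pearson method". Section 4.3.1.4 then adds: "Additional analyses of AEs will be included as part of the safety analyses".

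**Other AE summaries.** SAP 4.5.2.2 plans the following: "An overall summary of solicited and unsolicited AEs including subject counts, event counts, percentages (of subjects only) will be created". Under unsolicited AEs, a row labelled "Within 29 Days after Vaccination" appears once beneath SAEs and once beneath AESIs, with related SAEs and related AESIs on rows of their own. The system organ class and preferred term tables with a 29-day window are related-only, for example "Related SAEs Occurring within 29 Days of any Vaccination".

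**Declared changes.** SAP 4.7 lists two: the scope and timing of the primary analysis, and an added 6-fold response threshold. Neither concerns this endpoint.

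**The concern.** The endpoint and the analysis that appears to serve it differ in one word, and that word changes which subjects count. The missing filter in the endpoint looks deliberate, since the 8-day secondary endpoints and the neighbouring 29-day Grade 3 endpoint all carry one. The likeliest explanation is that the 8-day wording was carried over when the window was extended.

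The filter matters because the trial is open label and relatedness is the investigator's judgement. A count that ignores causality does not depend on that judgement. Events with no recorded causality add a further difficulty. SAP 4.5.2.2 says no causality will be imputed, whereas protocol 8.12 provisionally classes such events as possibly related. If the field is blank in the analysis data, an SAE would drop out of a related-only count but would still belong to the endpoint as defined.

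At stake is whether the report contains the figure that both documents name: the percentage of subjects with any SAE or AESI within 29 days.

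**Working it through.** The plan states no figure for this endpoint, so there is nothing to reproduce. The check compares texts, with arithmetic only for illustration.

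**1. Endpoint against analysis**

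| Item, 29 days | Protocol 1.3 and SAP 1.1 | SAP 4.3.1.4 | Match |
|---|---|---|---|
| SAE or AESI | any causality | related only | no |
| Grade 3 or higher AE | related only | related only | yes |

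The two analyses in 4.3.1.4 pair with the first two supportive endpoints in 1.1. Neither document lists a related SAE/AESI endpoint at 29 days.

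**2. What the overall summary in SAP 4.5.2.2 supplies**

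- *Causality:* related events have their own rows, so the 29-day rows beneath SAEs and AESIs are all-causality.
- *Combination:* SAEs and AESIs are separate, and a subject with both counts in both. If *a* subjects have an SAE and *b* have an AESI, the combined count lies between max(*a*, *b*) and *a* + *b*. With *a* = 2 and *b* = 3 it could be 3, 4 or 5. For n = 90 that is 3/90 = 3.3% to 5/90 = 5.6%, and the two rows cannot say which.
- *Scope:* the 29-day rows stand under unsolicited AEs. Solicited SAEs have rows of their own without a 29-day window.
- *Window:* a footnote runs the period after the last or single vaccination to the end of the Active Trial Period, whose visit window is 28 to 35 days. Counting the vaccination day as day 1, as the memory aid does, 29 days means the vaccination day plus 28. The rows can then run up to 35 − 28 = 7 days longer.
- *Interval:* none is mentioned.

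**3. Illustration of size**

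Inputs: approximate group sizes of 30, 90 and 90 (SAP 6). Event counts are assumed, because the documents give no SAE or AESI rates. The exact 95% limits for *x* of *n* are the 0.025 quantile of Beta(*x*, *n* − *x* + 1) and the 0.975 quantile of Beta(*x* + 1, *n* − *x*). For *x* = 0 the lower limit is 0 and the upper is 1 − 0.025^(1/*n*).

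Assume no related event, and *x* subjects with any SAE or AESI:

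| n | x | Percent | 95% limits |
|---|---|---|---|
| 90 | 0 | 0 | 0 to 4.0 |
| 90 | 1 | 1.1 | 0.0 to 6.0 |
| 90 | 3 | 3.3 | 0.7 to 9.4 |
| 90 | 5 | 5.6 | 1.8 to 12.5 |
| 30 | 0 | 0 | 0 to 11.6 |
| 30 | 1 | 3.3 | 0.1 to 17.2 |

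The rows with *x* = 0 are what a related-only analysis would show. The others are the endpoint as defined. One subject is 1/90 = 1.1 percentage points in Groups 2 and 3, and 1/30 = 3.3 points in Group 1.

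**The case against.** The strongest reply is that 4.3.1.4 is an addition. The secondary estimand is about related events, so repeating it over a longer window naturally keeps the filter. The next sentence sends other AE analyses to the safety section, which holds the all-causality rows. The protocol also promises no interval here: 9.15 plans Clopper-Pearson limits for the 8-day endpoints, and 9.18 says other safety data are summarized descriptively. On that view no planned interval was dropped.

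Much of this stands. A reader might infer from 4.3.1.4 that the stated endpoint has been replaced by a smaller one and that unrelated events go unreported. The documents do not support that. All-causality 29-day counts and percentages are planned, as are all-causality SAE and AESI tables for the Active Trial Period and separate listings. Nor is the safety rate necessarily understated, because a rate labelled as related beside all-causality rows misstates nothing. It is not certain even that the 4.3.1.4 result is a strict subset. If the composite rule travelled with the repeated analysis, subjects leaving the trial because of any AE within 8 days would count as well. SAP 1.1 points the other way, since that rule "will only occur for these secondary endpoints. The remaining summaries for safety will be presented as collected".

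The unsolicited heading may also cost little: SAP 4.5.2.1 has solicited events meeting SAE criteria entered on the AE form as well, and the overview has an SAE row covering both kinds. Finally, the table shells are in a separate document and may contain a combined row.

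What the reply does not remove is the mismatch itself. The SAP names an endpoint in 1.1, and no section of its text specifies the combined count that would estimate it.

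**Conclusion.** The concern holds in this limited form. SAP 4.3.1.4 contradicts the endpoint in SAP 1.1 and protocol 1.3, and SAP 4.7 does not declare it. The consequence is that the combined all-causality subject count is not specified and that the only 29-day SAE/AESI estimate with an interval is the related-only one. The component counts remain available in 4.5.2.2 and no data are lost.

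The missing interval by itself is not a departure from the protocol. The numerical effect cannot be estimated from the documents: the figures above rest on assumed event counts and show only how far a related-only figure and the stated endpoint could differ. The conclusion also rests on the SAP text alone, without the table shells.

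Severity is minor. The endpoint is supportive, the trial has no hypothesis tests, and neither the primary nor the secondary estimands are affected.

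**What to change.** In SAP 4.3.1.4, give the 29-day SAE/AESI analysis the causality wording of SAP 1.1, with one combined count of subjects per group and its Clopper-Pearson interval. Keep the related restriction for Grade 3 or higher AEs, where it matches the endpoint, and keep related SAEs and AESIs as an additional row. In the same edit, say that these 29-day figures use events as collected, as SAP 1.1 implies, and which window applies, since the 4.5.2.2 footnote differs from a strict 29 days.

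If the related-only analysis is what the sponsor wants, declare and justify it in SAP 4.7, and state in 4.5.2.2 where the combined all-causality count will be reported.

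The cost is a short wording change and one table filter with an added row. No new data are needed.
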